5.6 Participant Withdrawal/Discontinuation Criteria

Discontinuation of study intervention does not represent withdrawal from the study.

As certain data on clinical events beyond study intervention discontinuation may be important to the study, they must be collected through the participant's last scheduled follow-up, even if the participant has discontinued study intervention. Therefore, all participants who discontinue study intervention prior to completion of the protocol-specified treatment period will still continue to participate in the study as specified in Section 7.1.4.

Participants may discontinue study intervention at any time for any reason or be discontinued from the study intervention at the discretion of the investigator should any untoward effect occur. In addition, a participant may be discontinued from study intervention by the investigator or the study PI if study intervention is inappropriate, the study plan is violated, or for administrative and/or other safety reasons. Specific details regarding procedures to be performed at study intervention discontinuation are provided in Section 7.1.5.3.

A participant must be discontinued from study treatment but continue to be monitored in the study for any of the following reasons:

- The participant or participant's legally acceptable representative requests to discontinue study treatment.
- Confirmed radiographic disease progression outlined in Section 7.1.2.9. Patients who are believed to be deriving benefit based on the discretion of the investigator and PI are allowed to continue.
- Any progression or recurrence of any malignancy, or any occurrence of secondary malignancy that requires active treatment. Exceptions to secondary malignancy include basal cell carcinoma of the skin, squamous cell carcinoma of the skin, new non-ulcerated primary melanoma <1 mm in depth with no nodal involvement, or carcinoma in situ (eg, breast carcinoma, cervical cancer in situ) that have undergone potentially curative therapy. Exceptions should be discussed with the study PI prior to continuing therapy or remaining in follow-up.
- Unacceptable adverse experiences as described in Section 5.2.2.

- The participant has a medical condition or personal circumstance which, in the opinion of the investigator and/or sponsor, placed the participant at unnecessary risk from continued administration of study treatment.
- The participant has a confirmed positive serum pregnancy test.
- Noncompliance with study treatment or procedure requirements
- Recurrent Grade 2 pneumonitis, and other AEs that may require treatment discontinuation per Section 5.2.2 (Dose Modification).
- Discontinuation of treatment may be considered for participants who have attained a confirmed complete response (CR) and have been treated for at least 8 cycles (at least 24 weeks), receiving 2 cycles of the combination including 2 doses of pembrolizumab and at least 80% of the planned doses of lenvatinib beyond the date when the initial CR was declared. These participants may be eligible for second course treatment described in Section 5.2.3.
- The participant is lost to follow-up
- Completion of 35 treatment cycles (approximately 2 years) with pembrolizumab and lenvatinib. Note: Participants experiencing a clinical benefit may continue on lenvatinib alone beyond this time point until unacceptable toxicity or disease progression upon study PI consultation and approval (See Section 5.2.3 for additional details).

Note: The number of treatments is calculated starting with the first dose. Participants who stop the combination after receiving 2 years of treatment may be eligible for retreatment if they progress after stopping study treatment provided they meet the requirements detailed in Section 5.2.3. Participants may be retreated in the Second Course Phase (Retreatment) for up to an additional 17 cycles (approximately 1 year).
- Administrative reasons

A participant may be discontinued from study treatment but continue to be monitored in the study for any of the following reasons:

- Discontinuation of trial treatment with pembrolizumab and lenvatinib may be considered for participants who have attained a confirmed CR and have been treated for at least 24 weeks, receiving at least 2 doses of pembrolizumab beyond the date when the initial CR was declared.

Note: The number of treatments is calculated starting with the first dose of pembrolizumab.

- Progressive disease and/or lack of clinical benefit.

Note: Participants will be permitted to continue treatment beyond RECIST 1.1-defined progression provided investigator-assessed clinical stability is observed, and the participant is tolerating study drug (Section 5.5.4). Treatment beyond PD may be permitted upon study PI consultation and approval.

Participant Withdrawal From the Study

A participant must be withdrawn from the study if the participant or participant's legally acceptable representative withdraws consent from the study.

If a participant withdraws from the study, they will no longer receive study treatment or be followed at scheduled protocol visits.

Specific details regarding procedures to be performed at the time of withdrawal from the study, are outlined in Section 7.1.4. The procedures to be performed should a participant repeatedly fail to return for scheduled visits and/or if the study site is unable to contact the participant are outlined below.

Lost to Follow-up

If a participant fails to return to the clinic for a required study visit and/or if the site is unable to contact the participant, the following procedures are to be performed:

- The site must attempt to contact the participant and reschedule the missed visit. If the participant is contacted, the participant should be counseled on the importance of maintaining the protocol-specified visit schedule.
- The investigator or designee must make every effort to regain contact with the participant at each missed visit (eg, telephone calls and/or a certified letter to the participant's last known mailing address or locally equivalent methods). These contact attempts should be documented in the participant's medical record.
- Note: A participant is not considered lost to follow-up until the last scheduled visit for the individual participant. The missing data for the participant will be managed via the prespecified statistical data handling and analysis guidelines.

5.7 Participant Replacement Strategy

A participant who discontinues from study intervention, withdraws, or is unevaluable due to inability to reach first intracranial assessment scan will be replaced. An anticipated 10% drop-out rate was accounted for in the sample size calculations for Cohort 1/Melanoma and Cohort 2/RCC. An extra 3 patients were estimated to obtain at least 27 analyzable patients in Cohort 1/Melanoma.

An extra 3 patients were estimated to obtain at least 29 analyzable patients in Cohort 2/RCC.

5.8 Clinical Criteria for Early Trial Termination

Early trial termination will be the result of the criteria specified below:

1. Quality or quantity of data recording is inaccurate or incomplete
2. Poor adherence to protocol and regulatory requirements
3. Incidence or severity of adverse drug reaction in this or other studies indicates a potential health hazard to participants
4. Plans to modify or discontinue the development of the study drug

In the event of Merck's decision to no longer supply study drug, ample notification will be provided so that appropriate adjustments to participant treatment can be made.

6.0 TRIAL FLOW CHART

6.1 Study Flow Chart

Trial Period:		Treatment Cycles ^a								EOT ^b	Post-Treatment			Notes
Treatment Cycle/Title:	Main Study Screening Visit	1	2	3	4	To be repeated beyond 8 cycles				Discon	Safety FU ^{b,c}	FU Visits	Survival Follow-Up	
						5	6	7	8					
Scheduling Window (Days):	-28 to -1		± 3	± 3	± 3	± 3	± 3	± 3	± 3	At time of Discon	30 and 90 days post discon	Every 12 weeks post discon	Every 12 weeks	
Administrative Procedures														
Informed Consent	X													Consent form can be signed at any time prior to any protocol-specific screening procedures being performed. Additional consent is required at initial disease progression per RECIST 1.1.
Inclusion/Exclusion Criteria	X													
Demographics and Medical/Surgical History	X													Significant medical/surgical history will be captured for last 10 years.
Prior and Concomitant Medication Review	X	X	X	X	X	X	X	X	X	X	X	X		Concomitant medications will be recorded for 90d after last dose (or for up to 120d after last dose for SAEs).
Pembrolizumab and Lenvatinib Administration		X	X	X	X	X	X	X	X					Pembrolizumab 200 mg Q3W with lenvatinib 20 mg QD; 21-d cycle
Post-study anticancer therapy status											X	X	X	All anticancer therapy will be recorded until time of death or termination of survival follow-up. If a clinic visit is not feasible, follow up information may be obtained via telephone or email.
Survival Status		X	X	X	X	X	X	X	X	X	X	X	X	
Clinical Procedures/Assessments														

Review Adverse Events		X	X	X	X	X	X	X	X	X	X			AEs: monitored up to 90d after last dose. SAEs and pregnancy: monitored up to 120d after last dose, or 30d after last dose if participant starts a new anticancer therapy, whichever is sooner
Full Physical Examination	X													To be performed within 7d of C1D1.
Directed Physical Examination		X	X	X	X	X	X	X	X	X	X	X	X	
Vital Signs and Weight ^d	X	X	X	X	X	X	X	X	X	X				BP and HR will be measured after the participant has been resting for 5 minutes. See Section 5.2.2.6 for management of hypertension and Section 7.1.2.4 for vital signs. Height is measured at Screening only.
ECOG Performance Status	X	X	X	X	X	X	X	X	X	X				
12-lead ECG	X													Single 12-lead ECG. Participants must be in the recumbent position for a period of 5 minutes prior to the ECG. Additional assessments may be performed if clinically indicated.
Laboratory Procedures/Assessments: analysis performed by LOCAL Lab ^g														
Pregnancy Test – Urine or Serum β-HCG	X	X	X	X	X	X	X	X	X	X	X			Performed within 10 days of C1D1 and prior to all subsequent scheduled visits. Every effort should be made to collect samples at the same time of day. LDH is only required at screening. Urine protein ≥2 requires 24-hour urine collection and D15 re-evaluation per Section 5.2.2.7. Pregnancy test for WOCP to be done within 72 hours days of C1D1.
PT/INR and aPTT	X													
CBC with Differential	X		X	X	X	X	X	X	X	X	X			
Comprehensive Serum Chemistry Panel	X		X	X	X	X	X	X	X	X	X			
Urinalysis	X		X	X	X	X	X	X	X	X	X			
T3, FT4 and TSH	X		X	X	X	X	X	X	X	X	X			
Efficacy Measurements														
Tumor Imaging (MRI brain ^e and CT Chest, Abdomen, Pelvis)	X		X		X				X	X		X	X	Prior scans performed within the screening period but before signing informed consent may be

														used. All imaging visits have a scheduling window of ± 7 d. Intracranial disease progression will be assessed by mRECIST 1.1. Extracranial disease will be assessed by RECIST 1.1. For participants who DC for reasons other than PD, imaging should be performed Q12W. Imaging at EOT is not required if the previous tumor imaging assessment was within 4 weeks prior to the EOT visit. Imaging of any anatomy that shows disease either at screening or in subsequent evaluations will be required and should be submitted.
Tumor Biopsies/Archival Tissue Collection/Correlative Studies														
Archival or Newly Obtained Tissue Collection	X													New tissue will be collected if the patient has a biopsy or resection for any reason while on study; a new consent will be obtained from the subject for use of part of the collected tissue for research.
Correlative Studies Blood Collection ^f		X	X	X			X			X				

a. Participants who continue treatment with lenvatinib beyond approximately 2 years (only if they experience clinical benefit until unacceptable toxicity or disease progression and upon Sponsor consultation and approval) will follow the same SOA except that thyroid labs beyond approximately 2 years will be performed per SOC or as clinically indicated.

b. If EOT visit occurs ~30 days from last dose of study treatment, a 30-day safety follow-up visit is not required. In this situation, all procedures required at the 30-day Safety Visit and EOT are performed once and entered into the EOT visit only. End of treatment will be defined as the date when the participant discontinues all trial treatments.

c. Safety FU will occur during 2 separate visits: 30 days AND 90 days after last dose. If the 90 day-safety FU visit falls within the same window as an imaging FU visit, these visits may be combined. All procedures required at the Safety FU visit at 90 days will be performed at the imaging FU.

d. BP should also be obtained 1 week after starting lenvatinib (can be done at home or by a community health care provider), then every 2 weeks for the first 2 months. BP can be then followed at least once monthly thereafter and may coincide with treatment visits.

- e. Brain MRI must be performed at screening. Brain MRI should then be performed at week 6, 12, and Q12W thereafter; following Week 102, imaging should be performed every Q24W, or sooner if clinically indicated. Brain CT scan should only be used when MRI is contraindicated. The same imaging technique regarding modality and the use of contrast should be used in a participant throughout the trial to optimize the visualization of existing and new tumors.
- f. Blood for correlative studies will be collected prior to C1, C2, and C3 as well at every 3rd cycle thereafter (ie. prior to C6, C9, C12, etc.).
- g. Review requirements in Table 6 when scheduling lab assessments

Abbreviations: AE = adverse event; BP = blood pressure; C1 = Cycle 1; CT = computed tomography; D1 = Day; DC = discontinue/discontinuing; ECG = electrocardiogram; ECOG = Eastern Cooperative Oncology Group; EOT = end of treatment; FT4 = free thyroxine; FU = follow-up;; INR = international normalized ratio; LDH = lactate dehydrogenase; LVEF = left ventricular ejection fraction; MRI = magnetic resonance imaging; PD = progressive disease; PE = physical examination; PT = prothrombin time; Q3W = every 3 weeks; Q9W = every 9 weeks; Q12W = every 12 weeks; Q24W= every 24 weeks; QD = once daily; mRECIST = modified Response Evaluation Criteria in Solid Tumors; RECIST = Response Evaluation Criteria in Solid Tumors; RR = respiratory rate; SAE = serious adverse event; T3 = triiodothyronine; TSH = thyroid stimulating hormone; UPCR=urine protein-to-creatinine; WOCBP = women of childbearing potential.

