3.2 Secondary Objectives & Hypotheses

- (1) Objective: To determine the best overall objective response rate of pembrolizumab in combination with lenvatinib by RECIST 1.1.

Hypothesis: The combination of pembrolizumab and lenvatinib will demonstrate both intracranial and extracranial anti-tumor activity in patients who are anti-PD-1/PD-L1- experienced.

- (2) Objective: To assess PFS and OS of patients with untreated melanoma or RCC brain metastases on pembrolizumab in combination with lenvatinib.

Hypothesis: The combination of pembrolizumab and lenvatinib will improve PFS and OS in patients who are anti-PD-1/PD-L1- experienced.

- (3) Objective: To determine the duration of brain metastasis response to pembrolizumab in combination with lenvatinib.

Hypothesis: The combination of pembrolizumab and lenvatinib will prolong the duration of intracranial response in patients who are anti-PD-1/PD-L1 inhibitor- experienced.

- (4) Objective: To determine the safety and rate of adverse events of pembrolizumab in combination with lenvatinib.

Hypothesis: The combination of pembrolizumab and lenvatinib will result in an improved CNS toxicity profile compared to the historical CNS toxicity profile seen with pembrolizumab monotherapy, including a decreased incidence of perilesional edema and radionecrosis.

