Brain metastases are a common cause of morbidity and mortality in patients with advanced solid tumors and develop in up to 40% of patients with metastatic melanoma, with an incidence of 30% in de novo metastatic melanoma and up to 75% at autopsy (Cagney et al., 2017; Sloan, Nock, & Einstein, 2009). Brain metastases occur in 4-17% of cases of RCC (Saitoh, Shimbo, Tasaka, Iida, & Hara, 1982; Sheehan, Sun, Kondziolka, Flickinger, & Lunsford, 2003). Melanoma and RCC brain metastases are typically managed with local therapy including SRS or surgical resection depending on the size and number of lesions and presence of neurologic deficits. While local therapy can be effective, it does not prevent local or distant recurrence and does not impact extracranial disease.

Although monoclonal antibodies targeting the immune checkpoint molecules CTLA-4 (ipilimumab) and PD-1 (nivolumab, pembrolizumab) are FDA-approved for front-line treatment of advanced melanoma, the efficacy of these drugs for untreated melanoma brain metastases was not established until very recently because this patient population was historically excluded from clinical trials. Studies in previously untreated melanoma brain metastasis show that intracranial response can range from 16% with ipilimumab (Margolin et al., 2012), 26% with pembrolizumab (Kluger et al., 2019), 20% with nivolumab (Georgina V. Long et al., 2017), and 55% with combination ipilimumab and nivolumab (Tawbi et al., 2018). Although intracranial response rates are the highest with ipilimumab and nivolumab therapy, 60% of patients had grade 3-4 toxicities, and 36% had neurologic toxicity of any grade (Tawbi et al., 2018). Furthermore, the increase in multimodality therapy with combination immune therapy and radiation therapy has increased the incidence of long-term complications for treatment, evident by rising rates of radiation necrosis (Kluger et al., 2019). Additionally, concerns over worsening peritumoral edema have limited therapy in symptomatic patients.

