4.2.3 Rationale for Endpoints

4.2.3.1 Efficacy Endpoints

Primary endpoint:

Best brain metastasis response rate (BMRR), defined as PR and CR per modified RECIST 1.1.

Secondary endpoints:

Best overall objective response rate, defined as PR and CR per RECIST 1.1.

PFS, defined as the time from start of study drug administration to the date of the first documentation of disease progression or death from any cause, whichever occurs first.

OS, defined as the time from start of study drug administration to date of death from any cause.

Duration of brain metastasis response, defined as the time from response to the time of the first documentation of intracranial disease progression.

Safety and rate of adverse events, particularly neurologic adverse effects, which include worsening of edema and development of radiation necrosis.

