5.2.2 Dose Modification and toxicity management

5.2.2.1 Dose Modification and toxicity management for immune-related AEs associated with pembrolizumab and combination therapy

AEs associated with pembrolizumab exposure, including coadministration with additional compounds, may represent an immunologic aetiology. These immune-related AEs (irAEs) may occur shortly after the first dose or several months after the last dose of pembrolizumab/combination treatment and may affect more than one body system simultaneously. Therefore, early recognition and initiation of treatment is critical to reduce complications. Based on existing clinical study data, most irAEs were reversible and could be managed with interruptions of pembrolizumab/combination treatment, administration of corticosteroids and/or other supportive care. For suspected irAEs, ensure adequate evaluation to confirm etiology or exclude other causes. Additional procedures or tests such as bronchoscopy, endoscopy, skin biopsy may be included as part of the evaluation. Dose modification and toxicity management guidelines for irAEs associated with pembrolizumab/combination treatment are provided in Table 3.

Attribution of Toxicity:

When study interventions are administered in combination, attribution of an adverse event to a single component is likely to be difficult. Therefore, while the investigator may attribute a toxicity event to the combination, to lenvatinib alone or to pembrolizumab alone, for adverse events listed in Table 3, both interventions must be held according to the criteria in Table 3: Dose Modification and Toxicity Management Guidelines for Immune-Related Adverse Events Associated with Pembrolizumab.

Holding Study Interventions:

When study interventions are administered in combination, if the AE is considered immune-related, both interventions should be held according to recommended dose modifications.

Restarting Study Interventions:

Participants may not have any dose modifications (no change in dose or schedule) of pembrolizumab in this study, as described in Table 3.

- If the toxicity does not resolve or the criteria for resuming treatment are not met, the participant must be discontinued from all study interventions.

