7.1.5.3.3 Survival Follow-up

Participants who experience confirmed disease progression or start a new anticancer therapy, will move into the Survival Follow-Up Phase and should be contacted by telephone every 12 weeks to assess for survival status until death, withdrawal of consent, or the end of the trial, whichever occurs first.

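### Hypothesis 4 expects less edema and radionecrosis than with historical pembrolizumab, but with no historical rate or window, AE review tied to last dose and crude frequencies, the trial cannot tell a true decrease from shorter observation

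*Combined protocol and SAP*

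**What the plan says.** Section 3.2, hypothesis 4, states that the combination "will result in an improved CNS toxicity profile compared to the historical CNS toxicity profile seen with pembrolizumab monotherapy". Two events are then singled out, the profile "including a decreased incidence of perilesional edema and radionecrosis". Section 4.2.3.1 puts the same two events in the safety endpoint: neurologic effects "which include worsening of edema and development of radiation necrosis". No rate, margin or collection window for the historical pembrolizumab series is given anywhere.

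The end of adverse-event (AE) collection is stated in several places, and they disagree:

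| Source | AEs end at | SAEs end at |
|---|---|---|
| 6.1 Study Flow Chart | 90 days after last dose ("AEs: monitored up to 90d after last dose") | 120 days |
| 7.2 | 30 days | 90 days |
| 7.1.5.3.1 | one Safety Follow-Up Visit at about 30 days | 90 days |
| 7.2.3.1 and 7.2.5 | not stated | 90 days |

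In the flow chart, the Review Adverse Events row is marked from cycle 1 through discontinuation and Safety FU, and is blank for FU Visits and Survival Follow-Up. Imaging continues in those columns. Sections 7.1.2.9.2 and 7.1.5.3.2 keep patients who stop without progression on 12-weekly scans, for disease status. After confirmed progression or new therapy, section 7.1.5.3.3 says that patients "should be contacted by telephone every 12 weeks to assess for survival status until death".

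Sections 8.1 and 8.3 plan frequency tables of AEs in all subjects, plus listings that give the onset time and duration of each recorded event. No time-at-risk method and no comparison with history is specified.

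**The concern.** The hypothesis is directional and its comparator is outside the trial, so the two incidences mean something together only if both were collected over comparable time in comparable patients. Two features prevent that check.

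First, each patient's AE observation equals time on treatment plus a short tail. A patient who stops at 3 months is watched for about 4 to 6 months; one who completes treatment is watched for about 2 years. A crude frequency treats them alike. The background section itself says that multimodality therapy "has increased the incidence of long-term complications for treatment, evident by rising rates of radiation necrosis", so events after the tail cannot be dismissed. A follow-up MRI may show edema or necrosis after routine AE review has ended, and nothing requires it to be recorded as an AE.

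Second, radionecrosis needs prior irradiation. Section 5.1.1 allows previous brain radiotherapy and section 5.5.4 allows radiosurgery (SRS) on study, but neither is required. Patients with no irradiated lesion still count in the denominator.

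At stake is the trial's only statement on whether adding lenvatinib improves CNS tolerability. A lower crude percentage could be read as confirming hypothesis 4 when it reflects only shorter observation or a diluted denominator.

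**Working it through.** The plan states no radionecrosis or edema rate, so there is no figure to reproduce. The check asks how large an apparent decrease could be if the true rate were unchanged.

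**Inputs from the documents.** Average treatment 1 year (section 1.0); AE tail of 30 or 90 days, taken as w = 1 or 3 months; up to 62 patients.

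**Assumptions, not in the documents.** Same true hazard in this trial and in history; constant hazard; historical capture to 24 months; 24-month incidence q of 10%, 20% or 30%; death ignored at first.

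**Formula.** λ = -ln(1 - q)/24 per month. Recorded incidence with treatment time T is 1 - exp[-λ(T + w)]. Apparent reduction is 1 - recorded/q.

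**T = 12 months:**

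| q | λ | 90-day tail (15 months) | Reduction | 30-day tail (13 months) | Reduction |
|---|---|---|---|---|---|
| 10% | 0.00439 | 6.4% | 36% | 5.5% | 45% |
| 20% | 0.00930 | 13.0% | 35% | 11.4% | 43% |
| 30% | 0.01486 | 20.0% | 33% | 17.6% | 41% |

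The range is roughly 33-45%. At q = 20% and 62 patients, this is 62 × 0.130 = 8.1 or 62 × 0.114 = 7.1 recorded events, against 62 × 0.20 = 12.4.

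**Dependence on treatment time.** With T = 6 months, the trial records 39-42% (90-day) or 30-33% (30-day) of the 24-month incidence. With T = 24 months there is no shortfall. If treatment time is exponential with mean 12 months before a cap at 24, it records 55-57% (90-day) or 48-49% (30-day). The loss therefore falls on patients who stop early.

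**Effect of death.** Section 4.2.1 gives 48% alive at 2 years in the historical pembrolizumab trial, so μ = -ln(0.48)/24 = 0.0306 per month. Cumulative incidence is λ/(λ + μ) × {1 - exp[-(λ + μ)t]}. A value of λ = 0.0135 gives 20.0% at 24 months, 14.8% at 15 and 13.4% at 13. The reductions become 1 - 14.8/20.0 = 26% and 1 - 13.4/20.0 = 33%. Ignoring death overstates the size, but the shortfall remains.

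**Matched case.** If history used the same tail with similar treatment times, numerator and comparator shrink together and the apparent reduction is nil.

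**Dilution.** If a fraction f of patients have an irradiated brain lesion, the all-subject frequency of radionecrosis is f times the incidence among them. The documents give no f for either series, so this effect cannot be sized.

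**The case against.** The strongest reply is that no bias has been demonstrated, and that is right. A downward bias needs a historical series observed for longer, and its AE window is not given. Its 2-year survival figure does not supply one: this protocol also estimates survival at 1 and 2 years (8.3) while ending AE review at 30 or 90 days.

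There are real safeguards too. AEs are reviewed every cycle for up to 2 years of treatment. Late SAEs judged related are reportable without time limit (7.2, 7.2.5). AEs above Grade 1 are followed to Grade 0-1 or new therapy (7.1.5.3.1). The 90-day safety visit may be combined with an imaging visit in the same window (flow chart, note c). Only descriptive tables are planned.

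These points limit the size of the problem without removing it. The late-SAE route is passive and misses events that are not serious, or that are attributed to radiation. Following known events does not detect new ones. Combining visits covers one scan at most. Onset times of recorded events do not supply time at risk. And the descriptive tables would be the only evidence on a directional hypothesis.

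Some stronger inferences are tempting but not supported. A reader might conclude that:

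- the plan will produce a spurious decrease; this depends on the unstated historical window.
- the apparent reduction could reach 68%; that needs an assumed 6 months on treatment with the 30-day tail (1 - 6.3/20), against the stated average of 1 year.
- early progressors are the likeliest to receive SRS; no section says so, and 5.5.4 allows SRS with continued treatment.
- immune-related events that "may occur shortly after the first dose or several months after the last dose of pembrolizumab/combination treatment" include radionecrosis; that sentence in 5.2.2.1 is general.
- nothing but telephone contact happens after progression; 7.1.5.3.3 says that, but the flow chart marks imaging and directed examination in the Survival column.

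**Conclusion.** The point holds as a limit on interpretation. As written, the trial cannot separate a true decrease in edema or radionecrosis from shorter observation, or, for radionecrosis, from a denominator that includes patients never irradiated. The direction and size of any bias are unknown, because they depend on a historical rate and window that the documents do not state. The illustrative reduction of roughly 33-45% rests on a constant hazard, 24-month historical capture, 12 months on treatment, 24-month incidence of 10-30% and no competing death. It should not be quoted as an estimate of bias. The 30- versus 90-day conflict for AEs and the 90- versus 120-day conflict for SAEs are plain inconsistencies whatever view is taken of the rest. The sponsor should act on this point; it does not affect the primary endpoint.

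**What to change.** (a) Reconcile the AE windows (30 versus 90 days) and the SAE windows (90 versus 120 days) across 6.1, 7.1.5.3.1, 7.2, 7.2.3.1 and 7.2.5.

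(b) Record radionecrosis and perilesional edema, with any intervening SRS, from every follow-up brain MRI already scheduled.

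(c) In 8.3, report each event as cumulative incidence at fixed times, for example 6, 12 and 24 months, with death as a competing event. Report radionecrosis among patients with an irradiated brain lesion, with those irradiated on study entering at that date. State how patients who leave the imaging schedule at progression are censored, since that censoring may be informative.

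(d) State the historical rate with its capture window and compare only over a matched window. Otherwise restate hypothesis 4 as descriptive, with no conclusion of decreased incidence from crude rates.

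The cost is a little extra data entry at scans already planned, some SAP wording, and a less ambitious hypothesis. Active AE review by telephone to the end of the study, regardless of new therapy, is not needed for this. Calls cannot detect asymptomatic MRI findings, attribution after new therapy is less clear, and longer capture than in the historical series could bias the comparison the other way.
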